#### **4.8 HIV Seroconversion**

Frequent testing for HIV acquisition during the study period will allow prompt cessation of study drug in an HIV-infected participant, minimizing the risk that resistant virus will emerge. Therefore, HIV testing will be performed at all monthly study visits. HIV rapid testing and specimen collection will be completed prior to administration of study medication. Participants who have any reactive or positive HIV test result after initiating PrEP will be instructed to discontinue study drug immediately and will have further testing to clarify their HIV infection status, as described in Section 5.3. Any enrolled participant who is confirmed to have acquired HIV infection during the study will permanently discontinue study product and will be transitioned to a local HIV care clinic for appropriate follow-up and clinical management. Procedures for participants who acquire HIV infection are described in Section 5.3.

#### **4.9 Dose Modification**

Study personnel will record all events of participants who vomit immediately after dosing. Participants will not be asked to re-dose, unless they are confident that a recurrence of vomiting can be avoided. Additionally, re-dosing will only be allowed if an intact tablet is visible in the emesis. The same directly observed dosing rules will apply if re-dosing is attempted. Dose modifications of up to 3 sequential missed doses will be allowed if a participant has, for example, an acute gastrointestinal illness. Further dose modifications or other dose modification issues will be discussed with the PSRT. The PSRT may decide on further missed doses, or participant withdrawal from the study.

### **5 STUDY PROCEDURES**

An overview of the study visits and procedures schedule is presented in Table 5. Presented below is additional information on visit-specific study procedures.

#### **5.1 Screening Procedures**

**Screening for COVID-19 symptoms and protection measures:** We will follow the standard of care of the Kenya Ministry of Health, KEMRI, and WHO guidelines on the COVID-19 virus. Participants will be informed about practicing good hand hygiene, masking, good respiratory hygiene, and maintaining social distancing. Staff will adhere to social procedures including maintaining a six foot distance and wearing masks. Unvaccinated participants and staff will be screened for COVID-19-related symptoms when they arrive at the clinic using a checklist to check for risk of COVID-19 exposure based on symptoms or contacts. Any person that comes to the clinic with symptoms consistent with COVID-19 that include 1 or more of fever, cough (dry or productive), dyspnea, or myalgias will be isolated. Participants will be educated about the Ministry of Health specified measures for seeking healthcare during this time. Referral

mechanisms to local public health facilities are in place. Finally, the clinical site will maintain a register of all visitors and participants who enter the study site, to support usual care contact tracing efforts where necessary.

At the screening visit a qualified study clinician will perform a history and physical exam for each participant. A complete medication history will be obtained including all drug allergies, immunization history, prescription, over the counter, and herbal treatments. Vital signs will include height, weight, blood pressure, pulse, respiratory rate and temperature. The following procedures will be conducted:

- Informed consent
- Safety Labs: Complete blood count (CBC, specifically hematocrit and hemoglobin), HBV surface antigen, serum creatinine)
- HIV antibody (rapid test or blood)
- Urine pregnancy test
- Medical, medication, vaccine history
- Physical exam

A screening test(s) may be repeated within the 30-day screening window. A participant who is unable to schedule a study entry visit within the 30-day screening window must be re-screened prior to entry into the study. Participants who have not been immunized for HBV will be offered vaccination, as per standard of care. An HBV Antibody test may be ordered for participants who are unsure of their vaccination history.

## **5.2 Enrollment and Follow up Procedures**

Up to 54 evaluable HIV uninfected participants will be enrolled and followed up for 18 weeks: 10 weeks with DOT PrEP and up to 8 weeks for post drug kinetics sampling, with one visit at one week following dose cessation and an additional visit to occur between weeks 12 to 18. Enrollment must occur within 30 days of screening. An eligible participant who is unable to schedule a study entry visit within the 30-day screening window must be re-screened prior to entry into the study. All enrolments will be scheduled on specific days to avoid confusion in implementing the proposed dosing and sampling scheme. An adverse event questionnaire and medical and medication review will be conducted at each visit from study entry (enrollment) through week 10. Safety labs and vitals can be ordered as needed at any visit.

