## ***The Women TAF-FTC Benchmark Study***

### **Safety and Pharmacokinetics of TAF-FTC Pre-exposure Prophylaxis in Kenyan Cisgender women**

#### **PROTOCOL SCHEMA**

**Full Title:** **Safety and Pharmacokinetics** of TAF-FTC Pre-exposure Prophylaxis in African Cisgender women

**Short Title:** The Women TAF-FTC Benchmark Study

**Clinical Phase:** IIb

**Principal Investigators:** [name], PhD, [name].

**Purpose:** To assess the safety and define blood and tissue benchmark concentrations of Tenofovir (TFV) and Tenofovir diphosphate (TFV-DP) in cisgender women using directly observed tenofovir alafenamide (TAF)-emtricitabine (TAF-FTC) PrEP. These data will help guide accurate interpretation of efficacy results obtained in HIV prevention trials and programs in cisgender women.

**Study design:** An open-label, randomized, three-arm, directly observed therapy, pharmacokinetics study. HIV-uninfected non-pregnant cisgender women will be randomly assigned 1:1:1 to 1 of 3 dosing frequencies of DOT TAF-FTC PrEP: 2, 4, or 7 doses/week to help differentiate poor and modest adherence from perfect adherence. Drug concentrations in blood, cervico-vaginal fluid, and tissue will be measured during the study. The frequency of adverse events will be described.

**Study population:** The study will enroll 18-30 years old HIV uninfected, non-pregnant Kenyan cisgender women at low risk of HIV.

**Study site:** The Kenya Medical Research Institute-Thika Research Site, Thika, Kenya

**Study regimen:** Volunteers will receive 25 mg TAF/ 200mg FTC according to the dosing regimens outlined in the study design.

**Study duration:** The study will last for up to approximately 18 weeks for each participant. Recruitment, enrollment, and follow up will continue for approximately 2 years.

**Hypothesis:** TFV and TFV-DP dose-response thresholds from DOT TAF-FTC PrEP dosing for cisgender women will be defined but will differ from thresholds defined for TDF-FTC PrEP

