**Clinic visit 12: Week 10 Dose 70) visit:**

- HIV rapid test
- Study bloodwork: WB, DBS, PBMC, plasma
- Finger stick for DBS
- Study urine
- Safety Labs: Creatinine
- STI testing
- Medical, sexual, contraception, antenatal and vaccine history review
- AE assessment
- Concomitant Medication Review
- DOT

**Clinic visit 13: Post DOT PrEP visits (one week following dose cessation):** One visit at least 48 hours after the last DOT PrEP dose.

- Study bloodwork: WB, DBS, PBMC, plasma
- Study urine

**Clinic visit 14: Post DOT PrEP visits (Week 12-18):** One visit at least 14 days after visit above (i.e., the visit can occur any time between 2-8 weeks after the last DOT F/TAF PrEP which is between about week 12 and week 18 since enrollment)

- Study bloodwork: WB, DBS, PBMC, plasma
- Study urine
- Hair collection

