## **6.9 Reporting Requirements for this Study**

For each study participant, the SAE/EAE reporting period begins at Enrollment (Day 0) and ends when the participant's follow-up in the study ends. All reportable SAEs occurring during the study reporting period will be reported to the principal investigator

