## 7.3 Data Analysis

### 7.3.1 Primary outcomes

**Primary outcome 1:** The goal is to describe the frequency of adverse events, including emergent HIV infection during the study period. We will conduct a descriptive analysis for meeting PrEP157 eligibility among participants. The distribution of demographics and graded adverse events will characterize by overall and study arms and proportions will be compared between study arms using chi-square statistics.

**Primary outcome 2:** The goal is to quantify the effect of dose on steady state TFV-DP in DBS and PBMC based on an incomplete block design.  $C_{ss}$  (drug concentration at steady state) will likely require a normalizing log transform, such that geometric means and CIs will be reported. Dose proportionality will be assessed using the power model (on the natural log scale)  $\ln(Y_{ijk}) = \mu + S_i + P_j + \beta \log(D_k) + \varepsilon_{ijk}$  (Eqn. 1). Where  $Y_{ijk}$  is the response,  $C_{ss}$ , for the  $k$ th dose ( $k=2, 4, 7$  doses/week),  $j$ th period ( $j=1,2$ ),  $i$ th subject ( $i=1, \dots, 45$ );  $\mu$  is the overall mean,  $S_i$  is a random subject effect,  $P_j$  is the period effect and  $\varepsilon_{ijk}$  is random error. Dose proportionality dictates that  $\beta=1$  for dose-dependent parameters and we will assume dose proportionality if the 90% CI is contained within the limits (0.8, 1.25). The SAS mixed procedure will be utilized for model (Eqn 1), again assuming a random subject effect. Although we do not anticipate a period effect, our design allows us to test this effect. For the primary analysis, we assume no effect of 'non-daily dosing' regimens; although this will be examined in a secondary analysis. If dose proportionality is not shown, we will examine proportionality separately for each of the "non-daily dosing" dosing regimens. If dose proportionality is still not demonstrated when adherence regimens are examined separately we will consider dose as a categorical predictor.

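### Scheduled adverse event questioning stops at week 10, while follow-up, SAE reporting and an undefined safety window continue to weeks 12–18

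*Combined protocol and SAP*

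**What the plan says.** **Schedule of AE questioning.** Section 5.2 sets it out in one sentence: "An adverse event questionnaire and medical and medication review will be conducted at each visit from study entry (enrollment) through week 10". Table 2 marks AE assessment from entry to visit 12 (week 10), and concomitant medication review ends at the same visit. The visit lists in Section 5.2.2 include an AE assessment at each of visits 2 to 12. Visit 13 lists only bloodwork and urine; visit 14 lists bloodwork, urine and hair.

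**Length of follow-up.** The schema says "The study will last for up to approximately 18 weeks for each participant", and Section 5.2 divides this into "10 weeks with DOT PrEP and up to 8 weeks for post drug kinetics sampling". Visit 13 is planned for about one week after dosing ends ("One visit at least 48 hours after the last DOT PrEP dose"). For visit 14, "the visit can occur any time between 2-8 weeks after the last DOT F/TAF PrEP".

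**Safety reporting and outcome.** Under Section 6.9, "the SAE/EAE reporting period begins at Enrollment (Day 0) and ends when the participant's follow-up in the study ends". Section 7.3.1 gives the goal of primary outcome 1 as describing the "frequency of adverse events, including emergent HIV infection during the study period". No section defines that period or restricts the safety analysis to time on drug.

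**A general statement pointing the other way.** The opening paragraph of Section 5.2.2 says that AEs are assessed at the protocol-specified clinic visits, with no limit by week.

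**The concern.** Safety is the first primary objective, and Section 6.3 asks for every clinical AE of Grade 1 or higher to be recorded. Mild events are the ones a participant is least likely to report unless asked. If questioning stops at week 10 but the outcome is counted to the end of follow-up, the reported frequency mixes two methods of ascertainment: solicited up to week 10, and largely participant-initiated afterwards. A low count after week 10 could then reflect fewer events or less asking, and the data could not separate the two.

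The timing of visit 14 adds to this. It may fall anywhere in a six-week span, so the length of the less closely observed period differs between women, while Section 7.3.1 plans simple proportions by arm with no stated window.

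The plan also gives staff two instructions. Someone working from Table 2 or the visit lists would not ask about AEs at visits 13 and 14; someone working from the opening of Section 5.2.2 would.

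**Working it through.** **Inputs**
- Dosing period: 10 weeks (Section 5.2).
- Post-dosing follow-up: 2 to 8 weeks, ending at visit 14 (Sections 5.2 and 5.2.2).
- Last scheduled AE questionnaire: week 10 (Section 5.2, Table 2, visit lists).
- Half-life of TFV-DP in dried blood spots (DBS): about 17 days (Section 5.2.1).
- Participants: 54 (Section 2.6).

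**Step 1. The plan's own figures.** 10 + 8 = 18 weeks, as stated. The visit 14 window is 10 + 2 = 12 to 10 + 8 = 18 weeks, also as stated. With first-order accumulation, the fraction of steady state at day 70 is 1 − 2^(−70/17) = 94%, loosely consistent with the approximately 90% in Section 5.2.1.

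**Step 2. Share of follow-up without a scheduled questionnaire**
- Visit 14 at week 12: 2/12 = 17%.
- Visit 14 at week 18: 8/18 = 44%.
- Over 54 women: 54 × 2 = 108 to 54 × 8 = 432 person-weeks, against 54 × 10 = 540 person-weeks of dosing.

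These use the nominal schedule and ignore visit windows, replacements and early withdrawals.

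**Step 3. DBS TFV-DP remaining after the last dose.** Fraction remaining = 2^(−t/T), with t in days and T the half-life. The protocol's value is T = 17. The range T = 14 to 21 is an assumption to show sensitivity; 21 days is about the value that gives exactly 90% of steady state at day 70.

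| Time after last dose | T = 17 | T = 14 to 21 |
|---|---|---|
| 1 week (planned visit 13) | 75% | 71–79% |
| 2 weeks (earliest visit 14) | 57% | 50–63% |
| 4 weeks | 32% | 25–40% |
| 8 weeks (latest visit 14) | 10% | 6–16% |

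The highest residual levels fall early in the unsolicited period. The 44% figure applies only to women followed to week 18, by which time about 10% remains, so it should not be paired with the 75% or 57%.

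**Step 4. The passages side by side.** The Section 5.2 prose, Table 2 and the visit lists all stop at week 10. Because the prose and the lists agree with the table, a table damaged in extraction does not explain the gap. The opening of Section 5.2.2 is broader, but it reads as a summary: the same paragraph mentions hair collection, which takes place at only some visits. It therefore does not establish AE assessment at visits 13 and 14, but it does conflict with the schedule as written.

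**The case against.** The strongest defence is that the plan does not abandon safety after week 10.

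- **Reporting remains open.** Section 6.3 gives participants a 24-hour number and records AEs that are reported or observed, with no end date. Section 3.6 provides a calendar for unsolicited AEs, Section 5.2 allows safety labs and vitals as needed at any visit, and Section 8.5 mentions interviews on tolerability and safety during the study. This stands. A reader might infer that AEs go unassessed after week 10; the documents support only a change from solicited to mainly participant-initiated reporting.
- **Known AEs are followed.** A reader might infer that resolution of earlier events is also left to spontaneous report. Section 6.3 contradicts that: anyone reporting an AE is followed clinically until it resolves or stabilizes. The gap concerns new events only.
- **The expected risk is early.** Section 8.4 places gastrointestinal intolerance typically in the first month, Section 8.5 describes side effects as self-limiting within 1–2 weeks, and the stated purpose of the later weeks is kinetic sampling. This lowers the number of events likely to be missed, but it cannot be confirmed if nobody asks.
- **Residual drug may not matter clinically.** A reader might infer from the 75% and 57% figures that women remain at meaningful toxicological exposure. The documents do not show this. They use DBS TFV-DP as an adherence marker, do not link it to toxicity, and give no plasma half-life.
- **The study period may mean dosing.** Section 4.8 uses the term in connection with stopping study drug. That reading is possible, and it is why a definition is needed.
- **The schedule is the same in every arm.** That is correct. No bias between arms is shown, and none is claimed here.

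**Conclusion.** The point holds as a mismatch between the AE schedule and the follow-up it serves. Scheduled AE questioning and medication review end at week 10, follow-up and SAE reporting continue to weeks 12–18, the window for primary outcome 1 is undefined, and a general sentence in Section 5.2.2 conflicts with the detailed schedule. For new AEs, ascertainment is participant-initiated rather than solicited for 17% to 44% of follow-up, depending on when visit 14 falls. This rests on the nominal schedule and on taking Table 2 and the visit lists as what staff will follow.

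The half-life calculation is supporting context only: about 75%, 57%, 32% and 10% of end-of-dosing DBS TFV-DP remains at 1, 2, 4 and 8 weeks, assuming first-order decline at 17 days. The mismatch stands without it.

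Sample size and the pharmacokinetic objectives are unaffected. The change is worth making because it improves ascertainment of a primary safety outcome at very little cost.

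**What to change.** 1. Add the existing AE questionnaire and concomitant medication review to visits 13 and 14 in the Section 5.2 text, the Section 5.2.2 visit lists and Table 2, so that all three agree with the opening paragraph of Section 5.2.2.
2. In Section 7.3.1, define the window over which primary outcome 1 counts AEs and emergent HIV infection, and state how follow-up of differing length is handled.
3. Tabulate AEs separately for the dosing and post-dosing periods, divided at each participant's actual last dose.

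If visits 13 and 14 are deliberately left without AE questioning, the minimum is to end the window of primary outcome 1 at week 10, report later events separately as participant-initiated, and align Section 5.2.2 with that choice.

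**Cost:** a few minutes at two visits that already take place, a small schedule amendment and one additional table split. No sample size or power figure changes.

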### **5.2.1 Dosing schedule and assessment of compliance**

The design of the study is guided by the ~17-day half-life of TFV-DP in DBS, and includes 10 weeks of dosing to achieve approximately 90% of steady-state, weekly sampling at convenience times (i.e., rather than troughs), and three dosing groups (2, 4, and 7 doses per week) to demonstrate dose-proportionality. All cisgender women will have 10 weeks of DOT PrEP to establish steady state in DBS and WB. We have chosen a dosing frequency scheme for non-daily doses to directly replicate the STRAND DOT study schedule based on the ~17-day half-life of TFV-DP in DBS: The 2 doses per week will be taken on Monday and Tuesday, and the 4 doses per week on Monday, Tuesday, Thursday, and Friday. This schedule will permit simultaneous evaluation of concentrations derived from intermittent and day-by-day dosing. The operationalization of specific days for dose taking can be adjusted prior to study start while maintaining the randomized adherence patterns (frequency of dosing taking) to permit efficient study operations and to minimize the burden on study participants. This is possible due to the long half-life of TFV-DP and planned sampling at steady state. Therefore, any chosen days would be appropriate.

All doses will be witnessed, as described above, in person by a study personnel in either a private room at the Thika clinic or at another predetermined location to maximize convenience for the participant. On dosing visits, the participant will take the dose by mouth and study personnel will ensure the tablet is swallowed by asking the participant to show that their mouth is empty. Flexible clinic scheduling will be available to promote high rates of follow-up and compliance and to minimize participants' burden. Where dosing cannot be witnessed in person, dosing will be witnessed over video via WhatsApp, Zoom, FaceTime, Skype, or other video-streaming device that is agreed upon by the participant and study

personnel. Only cisgender women with an active smart phone will be enrolled in this pharmacokinetics study to permit offsite observation of dose taking for the required DOT PrEP, and participants will be supported with commensurate data/internet bundles. A one-month supply of back-up medication will be provided to participants at study enrollment to be used if the participant is unable to attend their visit at the clinic. All doses taken offsite will be directly observed by study staff by live video streaming and participants will be asked to open their mouth afterwards to confirm swallowing. Dosing may occur at variable times within the assigned dosing day. All doses will be taken without regard to food, but meal information will be collected with each dosing event.

Study personnel will use a dosing log to document directly observed doses. Participants will be given a detailed calendar that shows scheduled dosing days. This schedule will also be reinforced when study personnel interact with participants.

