##### ***Blood***

A blood sample will be obtained at protocol specified visits to process plasma, whole blood, DBS, and PBMCs. On a given study day blood collection, up to 21mL of blood for study bloodwork will be drawn with no planned timing relationship with dosing. The blood will be collected from an arm vein by trained clinic staff according to study site policies and procedures.

The schedule of protocol visits and procedures are outlined in Table 2.

Table 2: Schedule of protocol visit schedule and procedures.

Timeline (weeks)	Screening	Entry	DOT PrEP Period (weeks)											Post DOT Period	
			W1		W2	W3	W4	W5	W6	W7	W8	W9	W10	W11	W12-18
			Day 4	Day 7											
Clinic Visits #		1	2	3	4	5	6	7	8	9	10	11	12	13	14
Procedure															
Informed consent	x														
Medical, sexual, contraception, antenatal history review, vaccine history	x	x	x	x	x	x	x	x	x	x	x	x	x		
Physical exam a	x														
Dispense back up PrEP medication e		x													
Issue medical calendar		x													
AE assessment		x	x	x	x	x	x	x	x	x	x	x	x		
Safety Labs a,c	x	[x]											x		
Urine βHCG a	x	[x]						x				x			
HBS Ag	x														
HIV-1 rapid test a	x	[x]						x			x				
Hair collection							x			x		x			x
hDNA	x		x												
Study Bloodwork d (WB, plasma, DBS, PBMC)*PBMC is collected bi-weekly		x	x	x	x	x	x	x	x	x	x	x	x	x	x
Vaginal tissue f			x	x			x					x			
Vaginal swab		x	x	x			x				x		x		
DBS by fingerstick			x	x			x				x		x		
Study Urine d		x	x	x	x	x	x	x	x	x	x	x	x	x	x
Concomitant Medication Review	x	x	x	x	x	x	x	x	x	x	x	x	x		
STI testing (CT,GC, syphilis, HSV-2)		x											x		
DOT b		x	x	x	x	x	x	x	x	x	x	x	x		

[x] Indicated if screening occurred more 30 days before planned enrollment. The screen and entry visits must be ≤ 30 days apart.

a. Safety labs or vitals can be performed as needed at any time

b. DOT performed if applicable per randomization schedule

c. Protocol-specified safety labs include: CBC, HbAg, Creatinine clearance, in addition to monthly HIV testing and urine pregnancy tests.

d. Study Bloodwork: WB, DBS, PBMC, plasma and all available blood cell types; Study Urine: endogenous molecules such as nucleosides.

\*PBMC is collected bi-weekly (baseline, week 2, 4, 6, 8, 10)

e. Study medications will be dispensed as described

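### The dose-proportionality test ignores when in the weekly dosing cycle blood is drawn; if draws cluster on one weekday, a truly proportional drug can fail the 0.8 to 1.25 rule, modestly in DBS and to an unknown degree in PBMC

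*Combined protocol and SAP*

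**What the plan says.** Section 5.2.1 sets out the sampling as "weekly sampling at convenience times (i.e., rather than troughs), and three dosing groups (2, 4, and 7 doses per week) to demonstrate dose-proportionality". It fixes the dosing days: "The 2 doses per week will be taken on Monday and Tuesday, and the 4 doses per week on Monday, Tuesday, Thursday, and Friday"; the third arm doses daily (Section 2.5). It adds that the days may be changed before the study starts: "This is possible due to the long half-life of TFV-DP and planned sampling at steady state. Therefore, any chosen days would be appropriate". The only half-life given is about 17 days, for DBS, and steady state is claimed for DBS and whole blood.

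Under Blood in Section 5.2.3.1, "up to 21mL of blood for study bloodwork will be drawn with no planned timing relationship with dosing". Section 9.1 repeats this and makes only the entry sample pre-dose. Section 5.2.2 allows each visit a window of up to 10 days, longer than the 7-day dosing cycle.

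For Primary outcome 2 in Section 7.3.1, "The goal is to quantify the effect of dose on steady state TFV-DP in DBS and PBMC". The response Css enters a power model (Eqn. 1) with subject, period and log doses per week. The decision rule is "we will assume dose proportionality if the 90% CI is contained within the limits (0.8, 1.25"). The section adds: "For the primary analysis, we assume no effect of 'non-daily dosing' regimens". A nonlinear mixed model of concentration over time is planned in addition, but the rule is not attached to it.

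**The concern.** After its Tuesday dose the 2/week arm has no drug for six days, while the daily arm is topped up every day. A concentration drawn early in the week therefore flatters the 2/week arm, and one drawn late penalises it. Eqn. 1 can only read that difference as a departure from slope 1.

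Whether it averages out depends on the spread of draw days. Section 5.2 schedules enrolment on specific (unnamed) days, the first dose is given at entry, and visits follow in 7-day steps labelled Dose 7, 14, up to 70. Clustering on one weekday is therefore plausible. Averaging several weekly visits would not remove it, because they fall on the same weekday.

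At stake is the only stated decision rule in the primary pharmacokinetic analysis. A failed rule sends the analysis to separate regimens and then to categorical dose, both using the same values. Those values also feed the geometric means and the 25th-percentile cut points of Primary outcome 3.

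**Working it through.** **Inputs.** From the protocol: half-life h = 17 days in DBS, dosing days as above and 10 weeks of dosing (Sections 2.5 and 5.2.1); 18 women per arm and CV 25% (Section 7.4); limits 0.8 to 1.25 (Section 7.3.1). Assumed: one value per woman, all women drawn at the same point of the week, equal contribution per dose (exact proportionality) and, for PBMC, the half-life and CV 25%. Loading is run two ways, instant and with a 1-day half-time.

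**The plan's own figure.** The fraction of steady state is 1 − 2^(−t/17): 89.8% at day 56, 92.3% at day 63 and 94.2% at day 70. This agrees with the stated approximate 90%.

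**Slope.** With instant loading, the level at time T is the sum of 2^(−(T−t)/h) over past dose times t. The least-squares slope of ln(level) on ln 2, ln 4, ln 7 has weights −0.823, 0.057 and 0.767. With 1-day loading, each term becomes [kf/(kf−k)]·(e^(−ka) − e^(−kf·a)), where a = T − t, k = ln 2/h and kf = ln 2 per day.

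*DBS, Monday of week 11 before dosing.* Up to a factor common to the arms:
- 2/week: 2^(−7/17) + 2^(−6/17) = 0.752 + 0.783 = 1.535
- 4/week: add 2^(−4/17) + 2^(−3/17) = 0.850 + 0.885, giving 3.269
- daily: sum over ages 1 to 7 days = 5.966

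The logs are 0.428, 1.185 and 1.786. Slope = −0.353 + 0.067 + 1.370 = 1.084.

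**Chance of passing.** SD of log = √ln(1 + 0.25²) = 0.246. SE of the slope = 0.246/√14.18 = 0.0654, where 14.18 = 18 × the sum of squares of the three centred log doses. The 90% CI half-width is 1.675 × 0.0654 = 0.110, so the estimate must lie between about 0.910 and 1.140. Then P ≈ Φ((1.1405 − β)/0.0654) − Φ((0.9095 − β)/0.0654).

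| DBS draw, week 10, instant loading | Level vs own weekly average (2 / 4 / 7 per week) | Slope | P(pass) |
|---|---|---|---|
| Weekly average | 0 / 0 / 0% | 0.994 | 89% |
| Monday after dose | +1.7 / +0.2 / +1.2% | 0.989 | 88% |
| Tuesday after dose | +12.8 / +3.8 / +1.5% | 0.909 | 50% |
| Wednesday before dose | +8.3 / −0.4 / −2.6% | 0.909 | 50% |
| Friday before dose | −0.2 / −0.9 / −2.0% | 0.980 | 85% |
| Sunday before dose | −8.0 / −1.6 / −1.5% | 1.051 | 90% |
| Next Monday before dose | −11.7 / −5.6 / −1.2% | 1.084 | 80% |

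With 1-day loading the DBS range over the week is 0.95 to 1.05.

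**Where the nominal visit falls.** Counted from a Monday first dose, the Dose 70 visit is on Sunday or Monday. That is 5 to 6 days after the last dose in the 2/week arm, 2 to 3 days in the 4/week arm and 0 to 1 day in the daily arm.

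**PBMC.** At an assumed 5 days with instant loading, the Monday pre-dose levels are 0.814, 2.048 and 4.177, so the slope is 0.169 + 0.041 + 1.096 = 1.306.

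| Assumed PBMC half-life and loading | Slope, Sunday / Monday before dose | P(pass) |
|---|---|---|
| 7 days, instant | 1.14 / 1.21 | 52% / 14% |
| 7 days, 1-day | 1.07 / 1.14 | 86% / 53% |
| 5 days, instant | 1.20 / 1.31 | 18% / 1% |
| 5 days, 1-day | 1.10 / 1.19 | 75% / 21% |
| 3 days, instant | 1.36 / 1.54 | 0% / 0% |
| 3 days, 1-day | 1.18 / 1.34 | 27% / 0% |

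Over the whole week the slope leaves 0.8 to 1.25 below about 6 days with instant loading. With 1-day loading the range is 0.87 to 1.19 at 5 days and 0.85 to 1.25 at 4 days, so it leaves the limits only below about 4 days.

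**Even spread.** If draws are uniform over the week in every arm, the expected slope is about 1.00 in DBS and 1.01 to 1.02 in PBMC at 5 days.

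**The case against.** The strongest reply is that these figures are envelopes, not expected biases. No draw day is planned. Enrolment days are not named, dosing days may change, and a 10-day window can scatter draws over the whole cycle, in which case the slope hardly moves. Even a Monday draw gives 0.99 in DBS if the dose is taken first (instant loading). Section 4.8 can be read as putting specimen collection before dosing at the monthly visits, but it concerns HIV testing, and Section 9.1 disclaims any order. All of this stands: the documents do not show that a shift will occur. They also do nothing to prevent one, and the 7-day visit steps favour clustering.

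Second, the DBS slope stays inside the limits on every day, and at the end-of-cycle draw the chance of passing is close to that of the weekly average. This also stands. The 50% figure needs essentially all women drawn just after the Tuesday dose or on Wednesday before dosing.

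Third, the planned nonlinear model can use dose times, and a secondary analysis examines the non-daily regimens. Both help interpretation, but neither changes the rule, and the fallback analyses reuse the same values without separating draw time from true non-proportionality.

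A reader might infer that the PBMC test must fail if the half-life is 5 days or less. The documents do not support that. They give no PBMC half-life, loading rate or CV, and with 1-day loading the slope at 5 days stays inside the limits, although the chance of passing still falls.

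**Conclusion.** The point holds in a conditional form. The claim that any dosing days will do is not fully supported at the protocol's own DBS half-life and has no stated support for PBMC. If draws cluster on one weekday, true proportionality can be declared not shown. In DBS the loss is modest: an expected slope of 0.91 to 1.08, and a pass chance that falls to 50% only at the worst draw time. In PBMC it ranges from negligible to decisive, depending on a half-life and loading rate that the plan does not give. If PBMC behaved like DBS, the DBS figures would apply.

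All figures rest on first-order loss, equal contribution per dose, one shared draw time and one value per woman. The change is worth making because the rule as written can return a wrong answer and the remedy is cheap.

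**What to change.** 1. **Sections 5.2.2 and 5.2.3.1.** For the week-8 and week-10 draws in all arms, set a mid-cycle target day before any dose, about three days after the 2/week arm's second dose (Friday under the current schedule). Keep the 10-day window as a fallback: under Section 3.8 any missed pharmacokinetic sample triggers replacement, capped at 20% of 54, so a hard one-day window could cost evaluable women. Record clock times of dose and draw.

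2. **Section 7.3.1.** Keep Eqn. 1 on observed values. Before concluding that proportionality is not shown in DBS or PBMC, require the dose-frequency exponent to be estimated directly in the planned nonlinear mixed model with actual dose and draw times. For example, let the contribution per dose scale as (doses per week)^(β−1), and report β with its 90% CI. Do not feed the model's predicted weekly averages back into Eqn. 1: shrinkage, or linear kinetics built into the model, would pull them towards proportionality.

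3. **Section 5.2.1.** Limit the sentence on dosing days to DBS, and require the draw day to move with any change in dosing days.

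The target day alone is not enough. With instant loading, Friday before dosing gives slopes of 0.98 to 0.99 for half-lives of 3 to 7 days and 0.98 at 17 days. With 1-day loading it gives 0.97 (17 days), 0.94 (7 days) and 0.89 (3 days), hence step 2.

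The cost is slightly less flexible scheduling at two visits, recording draw times (a dosing log already exists) and a little more analysis. No new samples or visits are needed.
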